### 5.13.3 Vital Signs

Descriptive statistics for observed values and changes from baseline in the following vital signs will be presented by treatment group and visit:

- Systolic blood pressure (mmHg)
- Diastolic blood pressure (mmHg)
- Pulse rate (bpm)
- Body temperature (degrees Celsius)
- Body weight (kg)

In addition, a separate table presenting BMI and waist circumference will also be provided. A listing will be provided including all measurements.

For blood pressure and pulse rate, the orthostatic changes will be calculated as standing minus sitting readings. At each visit, the number of patients meeting the criteria for orthostatic hypotension as described in Section 5.2.11 will be summarized. Orthostatic changes will be listed separately, including a flag to identify cases of hypotension.

#### **5.13.4    Electrocardiogram Data**

Descriptive statistics for observed values and changes from baseline in the following ECG variables will be tabulated at each follow-up:

- Heart rate (bpm)
- PR interval (ms)
- RR interval (ms)
- QRS complex (ms)
- QT interval (ms)
- QTc interval (ms) [Bazett's formula - QTcB]
- QTc interval (ms) [Fridericia's formula - QTcF]

Shift tables in relation to the overall interpretation as provided by the central reader (Normal, Abnormal Not Clinically Significant (NCS), and Abnormal Clinically Significant (CS)) from baseline to each follow-up visit will be presented.

All ECG data, including details of any abnormalities, will be listed. For analysis purposes, the worst overall interpretation as recorded across triplicate assessments from the investigator will be reported. .

#### **5.13.5    Physical Examination**

The body systems within the physical examination data throughout the study will be summarized by treatment (Normal, Abnormal NCS, Abnormal CS). A shift table will be also presented, with shift from baseline to each post-baseline visit.

All PE data will also be listed.

#### **5.13.6    Placebo-Control Reminder Script (PCRS)**

Date and time of administration of the PCRS will be listed only.

#### **5.13.7    C-SSRS**

Suicidal ideation and suicidal behavior as measured by the C-SSRS will be summarized using frequencies and percentages by treatment group and timepoint. All C-SSRS data will also be listed.

### **5.13.8 Simpson-Angus Scale (SAS)**

Observed and change from Baseline values for the SAS will be provided by treatment group. Total scores as well as individual question responses and scores will be listed.

### **5.13.9 Abnormal Involuntary Movement Scale (AIMS)**

Observed and change from Baseline values for the AIMS will be provided by treatment group. Total scores as well as individual question responses and scores will be listed.

### **5.13.10 Barnes Akathisia Rating Scale (BARS)**

Observed and change from Baseline values for the BARS will be provided by treatment group. Total scores as well as individual question responses and scores will be listed.

### **5.13.11 Pregnancy Test**

Serum and urine pregnancy test data will be listed only.

## **6 INTERIM ANALYSIS**

No interim analyses are planned.

## **7 DATA AND SAFETY MONITORING BOARD ANALYSIS**

No DSMB is planned for this study. A Safety Review Committee (SRC) has been established to review ongoing safety data, and details for this are provided in a separate reporting plan.

## **8 CHANGES TO PLANNED PROTOCOL ANALYSIS**

The following changes were made compared to the protocol:

- Primary Estimand ([Section 2.3](#)): ‘Treatment Discontinuation prior to Week 4’ is no longer a relevant ICE and as such it has been removed from the estimand definition (see Table 1 and Table 2)
- Primary Estimand ([Section 2.3](#)): the primary analysis set has been changed to the ITT analysis set, with the caveat that should there be a substantial overlap with the mITT, the latter will instead be used as primary analysis set.
- Analysis Sets ([Section 5.1](#)): the PP Analysis Set and all associated analyses and summaries have been removed as non-informative.
- Site effect ([Section 5.11.4.2](#)): the rules for pooling study sites for analysis purposes have been slightly modified and the provision to formally test interactions has been removed (only summaries will be produced).
- Adverse Events ([Section 5.13.1](#)): the Poisson regression was changed to a log-binomial regression due to convergence and estimation issues observed when initially fitting the model,

due to data sparsity (i.e. SOCs/PTs with 0 subjects across most treatment arms showing the event).

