10.4.5.2 Adverse Events

AEs will be characterized by type, severity, seriousness, and relationship to treatment. AEs will be coded by preferred term and system organ class (SOC) using Medical Dictionary for Regulatory Activities (MedDRA) Version 23.0.

The incidence of TEAEs (number and percent of patients reporting the AE at least once during the study), SAEs, AEs related to study treatment, SAEs related to treatment, and AEs leading to study discontinuation will be summarized by treatment.

A TEAE is defined as any AE that has an onset on or after the dose of study drug, or any pre-existing condition that has worsened on or after the first dose of study drug.

Confidential Page 84 of 102

Any AE commencing after the last dose of study drug plus 14 calendar days will not be considered treatment-emergent.

The incidence of TEAEs and treatment-related AEs will also be summarized by maximum severity and strongest relationship to study drug by MedDRA primary SOC and preferred term. The summary will include the total number and percentage of patients reporting a particular event as well as the total number of events. In counting the number of events reported, a continuous event, i.e., reported more than once and which did not cease, will be counted only once; noncontinuous AEs reported several times by the same patient will be counted as multiple events.

Relative risks for the occurrence of any AE (i.e., at least 1 AE) during the course of the study as well as for each SOC/preferred term will be calculated for each LB-102 dose vs placebo alongside 95% CI and *P* values. For such analysis, a Poisson regression model with a log-link and a robust error variance will be considered, using the binary indicator for the presence of a given SOC/preferred term (or any AE) as response and treatment as the only covariate whose betas will be exponentiated to return the associated relative risk.

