In addition to the above summary tables, relative risks for the occurrence of any AE (i.e., at least 1 AE) during the course of the study as well as for each system organ class/preferred term will be estimated for each LB-102 dose vs placebo via a log-binomial regression model. For such analysis, the binary indicator for the presence of a given system organ class/preferred term (or any AE) will be used as response and the treatment group will be the only covariate, whose estimated regression coefficient will be exponentiated to return the associated relative risk, alongside their 95% CI and p-values. To such aim, the following sample SAS code will be used:

```
ods output estimates = rr;
proc genmod data =  descending;
  by aedecod aeterm;
  class subjid trt01an;
  model ae_binary = trt01an / dist = binomial link = log;
  estimate 'RR LB-102 50 mg vs. Placebo' trt01pn 1 0 0 -1 / exp alpha = 0.05;
  estimate 'RR LB-102 75 mg vs. Placebo' trt01pn 0 1 0 -1 / exp alpha = 0.05;
  estimate 'RR LB-102 100 mg vs. Placebo' trt01pn 0 0 1 -1 / exp alpha = 0.05;
run;
```

The above code assumes that the TRT01PN variable is ordered such that placebo is the last arm (i.e. TRT01PN = 4) and the others are sorted in ascending order, lowest to highest, and that AEDECOD and AETERM are the system organ class and preferred term variables, respectively.

All AEs will be listed.

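### Switching the adverse-event model from Poisson to log-binomial adds no estimable relative risk for terms with an empty arm, and SAP 5.13.1 has no rule for reporting such terms

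*SAP*

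**What the plan says.** Protocol 10.4.5.2 plans relative risks for each LB-102 dose against placebo: "a Poisson regression model with a log-link and a robust error variance will be considered", with "treatment as the only covariate whose betas will be exponentiated to return the associated relative risk".

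SAP 5.13.1 keeps the relative risk but has it "estimated for each LB-102 dose vs placebo via a log-binomial regression model". Again "the treatment group will be the only covariate", and the model line in the sample code is "model ae_binary = trt01an / dist = binomial link = log". The scope is wide: "relative risks for the occurrence of any AE (i.e., at least 1 AE) during the course of the study as well as for each" coded class and term.

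SAP Section 8 records the change ("the Poisson regression was changed to a log-binomial regression due to convergence and estimation issues observed when initially fitting the model") and gives data sparsity as the cause, described as "SOCs/PTs with 0 subjects across most treatment arms" showing the event.

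Section 5.13.1 sets no minimum number of events. It names no exact, penalised or profile-likelihood option and no zero-cell convention, and does not say how a relative risk that cannot be estimated is to be shown. In the list of outputs (SAP Section 10), Table 14.3.1.3 is still titled as a Poisson regression.

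**The concern.** The documented reason for a change of method should be something the change can remedy. Here the difficulty is empty cells, and the replacement has the same link and the same single factor as the model it replaces. If the set of estimable comparisons is unchanged, the SAP has swapped models without dealing with sparse terms.

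At stake is the planned relative-risk table for rarer events. The 100 mg arm is the most exposed because it has a third of the patients of each other arm. Without a rule, the table could carry numerical artefacts where it should say that no relative risk can be estimated, or those rows could be handled ad hoc after unblinding.

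**Working it through.** The documents give no figure for how many terms can be estimated, so there is none to reproduce. The check has four steps.

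**1. Algebra.** Let arm *i* have *a_i* events in *n_i* patients, with *i* = 0 for placebo. With one four-level factor, each model has one parameter per arm (it is saturated), so the fitted risk is *a_i/n_i* in both. Hence

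- RR = (*a_1/n_1*)/(*a_0/n_0*)
- SE(log RR) = √(1/*a_1* − 1/*n_1* + 1/*a_0* − 1/*n_0*), for log-binomial and for Poisson with robust variance alike.

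If *a_1* or *a_0* is 0, log RR is infinite and the SE is undefined.

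**2. Numerical fits.** Arms are assumed to be 108/108/108/36 (placebo/50/75/100 mg). This follows the 3:3:3:1 ratio, but the true sizes are redacted. The fits used Python, so the values at which SAS stops on divergent rows may differ.

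| Events (placebo/50/75/100) | Robust Poisson | Log-binomial |
|---|---|---|
| 10/15/20/8 | log RR 0.405, 0.693, 0.875; SE 0.3849, 0.3626, 0.4335 | identical |
| 0/2/3/1 | all three diverge: log RR about 21, SE about 46–48 | all three diverge: log RR about 21, SE about 16,400 |
| 3/0/2/0 | 75 mg: −0.405, SE 0.903; 50 and 100 mg diverge to about −21, SE 0.58–0.59 | 75 mg: identical; 50 and 100 mg diverge to about −22, SE about 18,000 and 31,000 |
| 0/0/0/1 | no valid RR | fit fails |

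The closed form agrees. For 15 against 10 events in arms of 108, √(1/15 − 1/108 + 1/10 − 1/108) = √0.1481 = 0.385.

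**3. How many relative risks survive.** Each term has three dose-versus-placebo comparisons. If placebo has no events, none is finite. If two arms are empty, at most one is finite. If three arms are empty, none is. The Section 8 description (zero in most of four arms) corresponds to three empty arms.

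**4. How often an arm is empty.** P(zero events) = (1 − *p*)^*n*. The inputs are assumptions: *n* = 75 to 120 per large arm, *n*/3 at 100 mg, and equal true incidence *p* in all arms. At *p* = 1%:

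- Placebo: 0.99^75 = 0.47 and 0.99^120 = 0.30.
- 100 mg: 0.99^25 = 0.78 and 0.99^40 = 0.67.

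The chance that a given relative risk is lost is 1 − (1 − *q_0*)(1 − *q_1*), where *q* is each arm's chance of zero events. For example, at 1% with 75 per large arm, 50 mg versus placebo gives 1 − 0.529² = 0.72.

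| True incidence | 50 or 75 mg vs placebo | 100 mg vs placebo |
|---|---|---|
| 1% | 51–72% | 77–88% |
| 2% | 17–39% | 50–69% |
| 5% | 0.4–4% | 13–29% |

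**The case against.** Several points on the other side stand and limit the finding.

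- **The two models do not fail in the same way.** With events on placebo and none on active drug, robust Poisson can print a log RR near −21 with an SE of about 0.58, which looks highly significant and is spurious. The log-binomial fit prints a huge SE and a Wald p-value near 1, which is visibly uninformative. A reader might infer that the switch achieved nothing. It removed a misleading output, but it added no estimable relative risk.
- **It would be too strong to say that no estimate or p-value can exist.** With events on placebo only, a point RR of 0 can be stated. With events on active drug only, the log-binomial likelihood still gives a likelihood-ratio test and a one-sided profile limit: 5/105 against 0/105 (assumed sizes) gives p = 0.008 and a lower RR limit of 2.2. The sample code in 5.13.1 requests neither, so the gap lies in the inference option and the reporting rule.
- **Terms seen only on LB-102 should not be read as the strongest signals.** Seven in ten patients receive LB-102. With no drug effect, a one-patient term falls only on LB-102 70% of the time and a two-patient term about 49% of the time (0.7²).
- **Nothing is hidden.** Section 5.13.1 tabulates numbers and percentages by term and lists all events. The multiplicity procedure covers only the primary endpoint, and no decision rule rests on these p-values.

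The objection does not rescue the Section 8 rationale: sparsity is given as the reason, and sparsity is left where it was.

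**Conclusion.** The point holds in this limited form. The change adds no estimable relative risk, because both models return the ratio of observed proportions and both diverge on exactly the same comparisons. This follows from the algebra and needs no assumption about arm size. As written, 5.13.1 would give a divergent estimate with a huge SE, or a failed fit, for each such comparison.

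The number of terms affected cannot be stated, since arm sizes are redacted and incidences unknown. Under the assumed sizes and equal incidence, about half to nearly nine-tenths of relative risks are lost at 1% incidence, and few at 5% outside the 100 mg arm. The documents do not support a reading that the safety analysis as a whole is compromised. This is a defect in a supplementary table and in its stated rationale, worth correcting before database lock.

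**What to change.** In SAP 5.13.1:

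- Keep the relative risk for a dose-versus-placebo comparison only where both arms have at least one event. Otherwise show it as not estimable.
- For every term, add the pairwise risk difference for each dose against placebo with a Miettinen-Nurminen score 95% CI, which exists with zero cells. At assumed sizes, 6/105 against 0/105 gives 2.1% to 11.9%, and 0/35 against 0/105 gives −3.6% to 10.0%.
- Align the variable names in the sample code: the CLASS and MODEL statements use trt01an, the ESTIMATE statements trt01pn.

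In Section 8, reword the rationale so that it does not imply that the log-binomial model resolves empty cells. In Section 10, retitle Table 14.3.1.3.

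The cost is one paragraph and a short piece of code. The SAP already uses PROC FREQ risk differences for CGI-S and PANSS response (5.11.5.1 and 5.11.5.5). The downside is a second effect measure beside the protocol's relative risk. A smaller change would keep the model with the not-estimable rule and request profile-likelihood limits. It would still give only one-sided information where one arm is empty, and none where both are.

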## 10 LIST OF TABLES, FIGURES AND LISTINGS

The following table includes details of the tables, figures and listings to be included within each section of the eCTD. The eCTD section is shown in bold. The following validation methods maybe used:

- Independent programming of numbers and manual review of format (IP)
- Independent programming by statistician of numbers and manual review of format (Stat IP)
- Manual review (MR)
- Code review (CR)

Table Number	Table Title	Validation Method	Shell Number (if repeat)
14.1	Demographics Data		
14.1.1	Disposition		
14.1.1.1	Patient Disposition – ITT Analysis Set	IP	
14.1.1.2	Screen Failures – Screened Set	IP	
14.1.1.3	Analysis Sets – ITT Analysis Set	IP	
14.1.1.4	Visit Attendance – Safety Analysis Set	IP	
14.1.1.5	Protocol Deviations – Safety Analysis Set	IP	
14.1.2	Demographics		
14.1.2	Demographics - Safety Analysis Set	IP	
14.1.3	Baseline Characteristics		
14.1.3.1	Previous Medical History – Safety Analysis Set	IP	
14.1.3.2	Medical History Ongoing at Screening – Safety Analysis Set	IP	14.1.3.1
14.1.3.3	Prior Medications – Safety Analysis Set	IP	
14.2	Efficacy Data		
14.2.1	Primary Efficacy Endpoint		
14.2.1.1	Primary Efficacy Endpoint, Change from Baseline to Week 4 in the PANSS Total Score, Primary Analysis – ITT Analysis Set	Stat IP	
14.2.1.2	Primary Efficacy Endpoint, Change from Baseline to Week 4 in the PANSS Total Score, Supportive Analysis – mITT Analysis Set	Stat IP	14.2.1.1
14.2.1.3	Primary Efficacy Endpoint, Change from Baseline to Week 4 in the PANSS Total Score, Sensitivity Analysis #1 (Re-mapped ET Assessments) – ITT Analysis Set	Stat IP	14.2.1.1
14.2.1.4	Primary Efficacy Endpoint, Change from Baseline to Week 4 in the PANSS Total Score, Sensitivity	Stat IP	

Table Number	Table Title	Validation Method	Shell Number (if repeat)
	Analysis #2 (Tipping-Point Analysis) – ITT Analysis Set		
14.2.1.5	Primary Efficacy Endpoint, Change from Baseline to Week 4 in the PANSS Total Score, Sensitivity Analysis #3 (Copy-Reference Imputation) – ITT Analysis Set	Stat IP	
14.2.1.6	Primary Efficacy Endpoint, Change from Baseline to Week 4 in the PANSS Total Score, by Baseline BMI – ITT Analysis Set	Stat IP	
14.2.1.7	Primary Efficacy Endpoint, Change from Baseline to Week 4 in the PANSS Total Score, by Baseline PANSS – ITT Analysis Set	Stat IP	14.2.1.6
14.2.1.8	Primary Efficacy Endpoint, Change from Baseline to Week 4 in the PANSS Total Score, Site Effect – ITT Analysis Set	Stat IP	
14.2.2	Secondary Efficacy Endpoints		
14.2.2.1.1	Secondary Efficacy Endpoint, Change from Baseline to Week 4 in the CGI-S Score – ITT Analysis Set	Stat IP	14.2.1.1
14.2.2.1.2	Secondary Efficacy Endpoint, Proportion of CGI-S Score Responders – ITT Analysis Set	Stat IP	
14.2.2.2	Secondary Efficacy Endpoint, Change from Baseline to Week 4 in the PANSS Positive Subscale Score – ITT Analysis Set	Stat IP	14.2.1.1
14.2.2.3	Secondary Efficacy Endpoint, Change from Baseline to Week 4 in the PANSS Negative Subscale Score – ITT Analysis Set	Stat IP	14.2.1.1
14.2.2.4	Secondary Efficacy Endpoint, Change from Baseline to Week 4 in the PANSS Marder Factor Scores – ITT Analysis Set	Stat IP	
14.2.2.5.1	Secondary Efficacy Endpoint, Proportion of PANSS Responders at Week 4 (Main Analysis) – ITT Analysis Set	Stat IP	
14.2.2.5.2	Secondary Efficacy Endpoint, Proportion of PANSS Responders at Week 4 (Sensitivity Analysis) – ITT Analysis Set	Stat IP	14.2.2.5.1
14.2.3	Exploratory Endpoints		
14.2.3	Exploratory Efficacy Endpoint, Change from Baseline to Week 4 in CogState Tests Total Scores – ITT Analysis Set	Stat IP	

Table Number	Table Title	Validation Method	Shell Number (if repeat)
14.3	Safety Data		
14.3.1	Displays of Adverse Events		
14.3.1.1	Overall Summary of Treatment-Emergent Adverse Events – Safety Analysis Set	IP	
14.3.1.2	Treatment-Emergent Adverse Events by System Organ Class and Preferred Term – Safety Analysis Set	IP	
14.3.1.3	Treatment-Emergent Adverse Events by System Organ Class and Preferred Term, Poisson Regression – Safety Analysis Set	Stat IP	
14.3.1.4	Treatment Related Treatment-Emergent Adverse Events by System Organ Class and Preferred Term – Safety Analysis Set	IP	14.3.1.2
14.3.1.5	Serious Treatment Emergent Adverse Events by System Organ Class and Preferred Term – Safety Analysis Set	IP	14.3.1.2
14.3.1.6	Treatment Emergent Adverse Events by System Organ Class and Preferred Term and Maximum Severity – Safety Analysis Set	IP	
14.3.1.7	Treatment Emergent Adverse Events by System Organ Class and Preferred Term and Strongest Relationship – Safety Analysis Set	IP	
14.3.1.8	Treatment Emergent Adverse Events Leading to Study Discontinuation by System Organ Class and Preferred Term – Safety Analysis Set	IP	14.3.1.2
14.3.2	Listings of Deaths, Other Serious and Significant Adverse Events		
14.3.2.1	Deaths – Safety Analysis Set	IP	
14.3.2.2	Serious Adverse Events – Safety Analysis Set	IP	
14.3.3	Narratives of Deaths, Other Serious and Certain Other Significant Adverse Events		
14.3.4	Abnormal Laboratory Values		
14.3.4	Abnormal Laboratory Values – Safety Analysis Set	IP	
14.3.5	Extent of Exposure, Dosage Information, And Compliance		
14.3.5.1	Treatment Exposure – Safety Analysis Set	IP	
14.3.5.2	Treatment Compliance – Safety Analysis Set	IP	
14.3.6	Vital Signs and Physical Examination		
14.3.6.1	Vital Signs – Safety Analysis Set	IP	
14.3.6.2	BMI and Waist Circumference – Safety Analysis Set	IP	14.3.6.1

Table Number	Table Title	Validation Method	Shell Number (if repeat)
14.3.6.3	Incidence of Orthostatic Hypotension – Safety Analysis Set	IP	
14.3.6.4	Physical Examination – Safety Analysis Set	IP	
14.3.6.5	Shift Table of Physical Examination to Day 28 – Safety Analysis Set	IP	
14.3.7	Other Safety		
14.3.7.1	Hematology – Safety Analysis Set	IP	14.3.6.1
14.3.7.2	Shift Table of Hematology – Safety Analysis Set	IP	
14.3.7.3	Chemistry – Safety Analysis Set	IP	14.3.6.1
14.3.7.4	Shift Table of Chemistry – Safety Analysis Set	IP	14.3.7.2
14.3.7.5	Urinalysis – Safety Analysis Set	IP	
14.3.7.6	Coagulation – Safety Analysis Set	IP	14.3.6.1
14.3.7.7	Hormones – Safety Analysis Set	IP	14.3.6.1
14.3.7.8	12-Lead ECG – Safety Analysis Set	IP	
14.3.7.9	Shift Table of 12-Lead ECG – Safety Analysis Set	IP	
14.3.7.10	Columbia – Suicidal Severity Rating Scale (C-SSRS) – Safety Analysis Set	IP	
14.3.7.11	Summary of Simpson-Angus Scale (SAS) Total Score – Safety Analysis Set	IP	
14.3.7.12	Summary of Abnormal Involuntary Movement Scale (AIMS) Total Score – Safety Analysis Set	IP	14.3.7.11
14.3.7.13	Summary of Barnes Akathisia Rating Scale (BARS) Global Score – Safety Analysis Set	IP	14.3.7.11
14.3.8	Concomitant Medication		
14.3.8	Concomitant Medications by ATC Level 2 and Preferred Name – Safety Analysis Set	IP	14.1.3.3
14.4	PK Tables		
14.4.1	Serum Concentrations, Descriptive Statistics – Pharmacokinetic Analysis Set	IP	
14.4.2	PK Parameters, Descriptive Statistics – Pharmacokinetic Analysis Set	IP	
14.4.3	Dose-Proportionality, Power Model Analysis – Pharmacokinetic Analysis Set	Stat IP	
14.5	PD Tables		
14.6	Other Data		

Figure Number	Figure Title	Validation Method	Shell Number (if repeat)
14.2	Efficacy Data		
14.2.1	Primary Efficacy Endpoint		
14.2.1.1	Primary Efficacy Endpoint, Line Plot of LS Means of Change from Baseline in PANSS Total Score – ITT Analysis Set	Stat IP	
14.2.1.2	Primary Efficacy Endpoint, Line Plot of LS Means of Change from Baseline in PANSS Total Score – mITT Analysis Set	Stat IP	14.2.1.1
14.2.1.3	Primary Efficacy Endpoint, Change from Baseline in PANSS Total Score at Week 4, Forest Plot of Subgroups Analysis – ITT Analysis Set	Stat IP	
14.4	PK Data		
14.4.1	Serum Concentrations, Mean Profiles on Linear Scale – Pharmacokinetic Analysis Set	IP	
14.4.2	Serum Concentrations, Mean Profiles on Semi-Logarithmic Scale – Pharmacokinetic Analysis Set	IP	
14.4.3	Serum Concentrations, Individual Profiles on Linear Scale – Pharmacokinetic Analysis Set	IP	
14.4.4	Serum Concentrations, Individual Profiles on Semi-Logarithmic Scale – Pharmacokinetic Analysis Set	IP	

Listing Number	Listing Title	Validation Method	Shell Number (if repeat)
16.2	Patient Data Listings		
16.2.1	Discontinued Patients		
16.2.1.1	Patient Disposition – ITT Analysis Set	IP	
16.2.1.2	Screen Failures – Screened Set	IP	
16.2.1.3	Visit Attendance – Safety Analysis Set	IP	
16.2.2	Protocol Deviations		
16.2.2	Protocol Deviations – Safety Analysis Set	IP	
16.2.3	Patients Excluded from The Efficacy Analyses		
16.2.3	Analysis Sets – ITT Analysis Set	IP	
16.2.4	Demographic Data		
16.2.4.1	Demographics – Safety Analysis Set	IP	
16.2.4.2	MINI 7.0.2 and BPD Module – Safety Analysis Set	IP	
16.2.4.3	Serology – Safety Analysis Set	IP	
16.2.4.4	Previous Medical History – Safety Analysis Set	IP	
16.2.4.5	Medical History Ongoing at Screening – Safety Analysis Set	IP	
16.2.4.6	Inclusion Criteria – Failures – Safety Analysis Set	IP	
16.2.4.7	Exclusion Criteria – Failures – Safety Analysis Set	IP	
16.2.4.8	Prior Medications – Safety Analysis Set	IP	
16.2.4.9	Concomitant Medications – Safety Analysis Set	IP	16.2.4.8
16.2.5	Compliance and / or Drug Concentration Data		
16.2.5.1	Study Drug Administration – Safety Analysis Set	IP	
16.2.5.2	Treatment Compliance – Safety Analysis Set	IP	
16.2.5.3	PK Concentration Data – Pharmacokinetic Analysis Set	IP	
16.2.5.4	PK Parameters – Pharmacokinetic Analysis Set	IP	
16.2.6	Individual Efficacy Response Data		
16.2.6.1	Positive and Negative Symptoms Scale (PANNS) – ITT Analysis Set	IP	
16.2.6.2	Clinician Global Impression-Severity (CGI-S) – ITT Analysis Set	IP	
16.2.6.3	CogState Tests – ITT Analysis Set	IP	
16.2.7	Adverse Event Listings		
16.2.7.1	Adverse Events – Safety Analysis Set	IP	
16.2.7.2	Adverse Events Leading to Study Discontinuation – Safety Analysis Set	IP	16.2.7.1
16.2.8	Individual Laboratory Measurements and Other Safety		
16.2.8.1	Abnormal Laboratory Values – Safety Analysis Set	IP	
16.2.8.2	Hematology – Safety Analysis Set	IP	
16.2.8.3	Chemistry – Safety Analysis Set	IP	16.2.8.2

Listing Number	Listing Title	Validation Method	Shell Number (if repeat)
16.2.8.4	Urinalysis – Safety Analysis Set	IP	16.2.8.2
16.2.8.5	Coagulation – Safety Analysis Set	IP	16.2.8.2
16.2.8.6	Hormones – Safety Analysis Set	IP	
16.2.8.7	Pregnancy Test – Safety Analysis Set	IP	
16.2.8.8	12-Lead ECG – Safety Analysis Set	IP	
16.2.8.9	Vital Signs – Safety Analysis Set	IP	
16.2.8.10	Orthostatic Vital Signs – Safety Analysis Set	IP	
16.2.8.11	Physical Examination – Safety Analysis Set	IP	
16.2.8.12	Placebo-Control Reminder Script (PCRS) – Safety Analysis Set	IP	
16.2.8.13	Columbia – Suicidal Severity Rating Scale (C-SSRS) – Safety Analysis Set	IP	
16.2.8.14	Simpson-Angus Scale (SAS) – Safety Analysis Set	IP	
16.2.8.15	Abnormal Involuntary Movement Scale (AIMS) – Safety Analysis Set	IP	
16.2.8.16	Barnes Akathisia Rating Scale (BARS) – Safety Analysis Set	IP
